### 72 Type of Compensation

*Click on the check box (or double click and type an "X" if using Google Docs) for each form of compensation that will be provided.*

**Cash**

**Check**

**Gift Card**

**Course Credit**

**ClinCard**

**Tango Card**

**Other**

*Describe, To input text, click in the light grey area below.*

### 73 Proration Schedule

*To input text, click in the light grey area below.*

Participants that are participating for course credit will receive .25 credits for every 15 minutes of participation in the study.

Participants not participating for credit will be entered into a different drawing for each part of the study they complete. The drawing for part 1 of the study will be for \$10. The drawing for part 2 of the study will be \$50. There will be 5 drawings for each part. Participants can receive up to \$60 that will be provided digitally through Venmo or Paypal.

**74**  **Amount of compensation and its form is reasonable for this population for the activities requested of them.**

**75 Costs**

*Click on the check box (or double click and type an "X" if using Google Docs) each applicable item regarding costs.*

|   |  |
|---|--|
|  Participants will have no costs associated with this study |  |
|  Standard of care procedures contributing to study data                |  Research procedures not associated with standard of care |
|  Administration of drugs / devices                                     |  Study drugs or devices                                   |
|  Transportation and parking  |  |

**76 Describe all costs below.**

*To input text, click in the light grey area below.*

Data analysis
Attention, Teleconferencing and Social Anxiety

Date: 12/05/2022

Identifiers: NCT04729803
Unique Protocol ID: STUDY00000106

Data Analysis

Describe the data analysis plan, including any statistical procedures or power analysis.

To input text, click in the light grey area below.

We will conduct multi-level models for all analyses (1) to compare the positive and negative interactions, where participants are looking, and social anxiety symptoms; (2) to compare the attention guidance condition to the other exposure groups using the Personal Report of Communication Apprehension as the primary outcome measure. We will use the brms package (Bürkner, 2018) in R to conduct Bayesian multi-level modelling.

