**\*All activities will be conducted online via Qualtrics and Gorilla.**

**Recruitment and Eligibility.** Participants ( $N=2,000$ ) will be recruited via a range of online recruitment methods including the research pool, social media, and email. We will recruit both male and female participants regardless of race or ethnicity. Potential participants will complete the study in two stages, all online.

**Stage 1 Procedures:** Participants will complete a series of questionnaires. Participants will be randomized to one of two groups if they are eligible for the second stage of the study.

**Positive Interaction.** Participants in this condition will be prompted with a question by audience members who were positive in their interactions with the other audience members.

**Negative Interaction.** Participants in this condition will be prompted with a question by audience members who were negative in their interactions with the other audience members.

At the end of this stage of the study participants will be able to choose whether they would like to continue to the intervention.

**Stage 2 (Intervention) Procedures.** Participants may be asked to wait 1-week prior to beginning the intervention. Participants will complete four intervention (i.e. exposure) sessions within two weeks. Participants will sign up for all four sessions at the start of the intervention.

For the first session:

- 1) Participants will receive a brief standardized psychoeducation module, presented via a video recording. This video will explain the intervention, its rationale, and the procedure.

For each subsequent session:

- 2) Participants will then complete up to 10 analogue teleconferencing calls, each lasting a maximum of two minutes. During each call participants will be prompted by one of the audience members.
- 3) Between speeches participants will have a 1-minute break.
- 4) Participants will complete the subjective units of distress scale (SUDS) before and after each speech trial.

**Attention Guidance Condition.** The experimental attention guidance condition consists of three unique components: (1) the intervention rationale will include information about the importance of visually attending to the faces of the audience; (2) participants will be given target audience members to focus their gaze on during their impromptu response. They will be told that they should look at and focus on the target audience member for the whole response.

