**Table 1. Measures and Assessment Schedule**

| Assessment       | Part 1
~30 min | Part 2:
Intervention
~30-45
minutes/session | 1-week
follow-up
~15 min | 2-Week
Follow-up
~15 min |  |
|------------------|-------------------|--|--------------------------------|--------------------------------|--|
| DEMO      | X                 |  |                                |                                |  |
| SCID-5-SR | X                 |  |                                |                                |  |
| TRT       | X                 |  |                                |                                |  |
| BAT       | X                 | X  | X                              | X                              |  |
| LSAS      | X                 | X  | X                              | X                              |  |
| PRCA-24   | X                 | X  | X                              | X                              |  |
| SATI      | X                 |  |                                | X                              |  |
| SUDS      | X                 | X  | X                              | X                              |  |
| EYE-TRACK | X                 | X  | X                              | X                              |  |
| OPEN      | X                 | X  | X                              | X                              |  |

*Note.* DEMO = demographics questionnaire (age, sex, etc.); SCID5-SR = Structured Clinical Interview for DSM-5; TRT = current treatment assessment; BAT = Behavioral Approach Task to assess peak fear, which will consist of giving a three-minute speech to an audience that is different from the audience during the intervention; LSAS = Leibowitz Social Anxiety Scale; PRCA-24 = Personal Report of Communication Apprehension; SATI = Speech Anxiety Thoughts Inventory; SUDS = subjective units of distress scale (e.g. peak fear); EYE-TRACK = Eye tracking data. OPEN = open-ended text boxes where participants can provide their impressions of the study

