### d Inclusion Criteria

*To input text, click in the light grey area below.*

Part 1: (1) Age 18-75, (2) fluent in English because the data collection materials have not yet been standardized in other languages, (3) having access to a computer with a webcam and ability to record audio

Part 2: Completed Part 1 + (1) Personal Report of Communication Apprehension > 55; (2) Leibowitz Social Anxiety Scale > 30 *and* Meets DSM-5 Criteria for Social Anxiety Disorder *or* Leibowitz Social Anxiety Scale > 60

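### Does randomising only those who pass the anxiety screen leave SAP analysis (1) unable to compare the positive and negative interactions?

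*SAP*

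**What the plan says.** The SAP (Data Analysis) gives analysis (1) one clause: multi-level models "to compare the positive and negative interactions, where participants are looking, and social anxiety symptoms". It names no symptom scale, time point, analysis population or model role for symptoms. PRCA is named as primary outcome for analysis (2) only.

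Protocol section 11 (Stage 1 Procedures) begins with questionnaires and then states: "Participants will be randomized to one of two groups if they are eligible for the second stage of the study". The two groups are the positive and negative interaction. Section 13d sets Part 2 eligibility as "Personal Report of Communication Apprehension > 55" together with "Leibowitz Social Anxiety Scale > 30 *and* Meets DSM-5 Criteria for Social Anxiety Disorder *or* Leibowitz Social Anxiety Scale > 60". Part 1 has no anxiety threshold: "Part 1: (1) Age 18-75, (2) fluent in English", plus a webcam and audio. After the interaction, "At the end of this stage of the study participants will be able to choose whether they would like to continue to the intervention".

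Table 1 marks LSAS and PRCA-24 once in Part 1 and again in Part 2 and at both follow-ups. BAT, SUDS and eye tracking are marked in the same four columns; SATI is marked in Part 1 and at 2 weeks. The table note reads "SUDS = subjective units of distress scale (e.g. peak fear"), so SUDS records momentary fear.

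**The concern.** Eligibility must be known before the Stage 1 randomisation, so the Part 1 LSAS and PRCA scores are baseline values. A positive-versus-negative comparison on them has an expected difference of zero. The next LSAS and PRCA scores belong to Part 2. They exist only in people who opted in after the manipulation, and are scheduled alongside the exposure intervention. If analysis (1) means symptoms as an outcome on these scales, one choice is uninformative and the other is open to selection bias.

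If symptoms are instead a predictor or moderator of gaze, the randomised sample is cut off from below on that variable, although the full range of anxiety was recruited. The worry is a weakened gaze-anxiety relation estimated on a fraction of the 2,000. One of the SAP's two analyses would be affected.

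**Working it through.** **1. The plan's own figure.** The only design number is 2,000 (section 14). It cannot be reproduced: no effect size, SD, error rate, power or dropout is given, and section 15 refers only to filling and completing Part 2. Nothing below depends on how it was chosen.

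**2. Order of events.** Questionnaires, then eligibility, then randomisation to an interaction, then the choice to continue. Part 1 LSAS and PRCA are therefore baseline values. SUDS, BAT, SATI and eye tracking do not decide eligibility, and the protocol does not fix their order relative to randomisation. Any of them recorded during or after the interaction is a post-randomisation outcome, taken before opt-in.

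**3. Effect of truncation.** Assumptions, since the documents give none: one normal anxiety score, the upper share p of 2,000 eligible, 1:1 allocation, full-sample gaze-anxiety correlation r = 0.30 in size. With a the (1 - p) normal quantile and λ = φ(a)/p:

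- SD ratio u = sqrt(1 + aλ - λ²)
- restricted correlation r' = r·u / sqrt(1 - r² + r²u²)
- slope standard error relative to all 2,000 = 1/(u·sqrt(p))
- smallest arm difference with 80% power, two-sided 5% = (1.960 + 0.842)·sqrt(2/n), n per arm = 1,000p; a frequentist yardstick only, as the SAP is Bayesian

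| p | n per arm | u | r' | SE ratio | Detectable difference (SD of outcome) |
|---|---|---|---|---|---|
| 10% | 100 | 0.41 | 0.13 | 7.7 | 0.40 |
| 20% | 200 | 0.47 | 0.15 | 4.8 | 0.28 |
| 30% | 300 | 0.51 | 0.16 | 3.6 | 0.23 |
| 40% | 400 | 0.56 | 0.17 | 2.8 | 0.20 |
| 50% | 500 | 0.60 | 0.19 | 2.3 | 0.18 |
| all | 1,000 | 1 | 0.30 | 1 | 0.13 |

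For p = 20%: a = 0.842, λ = 1.400, u = 0.468, r' = 0.145, SE ratio = 1/(0.468 × 0.447) = 4.8.

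**4. Correlation versus slope.** The SAP plans regression models, so the slope matters. In 2,000,000 simulated draws with p = 20%, the slope of gaze on anxiety was -0.30 in the full sample and -0.30 in the truncated one. The reverse regression, anxiety on gaze, fell from -0.30 to -0.07. Selecting on a predictor leaves a linear slope unbiased; selecting on the outcome does not. With r = 0.30 the gaze-on-anxiety standard error is sqrt(0.91)/sqrt(2,000) = 0.021 in everyone, and sqrt(0.91)/(0.468 × sqrt(400)) = 0.102 in the eligible 20%. A slope of that size is still 0.30/0.102 = 2.9 standard errors from zero.

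**5. One cut versus the real rule.** Eligibility is a joint rule on two scales, which truncates each one less. With two normal scores, equal cut-offs, correlation 0.3 to 0.9 between scales and 20% jointly eligible, u is 0.51 to 0.59, r' 0.16 to 0.18 and the SE ratio 3.8 to 4.4.

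**6. If follow-up symptoms were used.** With opt-in of 60% versus 40% by arm and a correlation of 0.3 between opt-in propensity and anxiety, the spurious arm difference is 0.3 × (0.966 - 0.644) = 0.10 SD. Both inputs are assumed. Equal opt-in with equal selection gives zero, and the documents give no opt-in rates by arm.

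**The case for a change.** The strongest case for a change is that section 36 describes the benefit as learning how teleconferencing affects social anxiety, so reading symptoms as an outcome of the interaction is natural. The sample spans all levels of anxiety, yet ineligible people are left out of the randomisation, and section 15 justifies the size by Part 2 alone. Randomising everyone would take one protocol sentence and one branching rule, and would shrink the slope's standard error considerably.

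Part of this stands. Part 1 LSAS and PRCA cannot be between-arm outcomes, and later scores do not give a clean comparison. The precision cost is real, and it also applies to an arm-by-anxiety interaction.

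The rest does not. Momentary fear and gaze are scheduled in Part 1, so the interaction can be compared on anxiety without LSAS or PRCA. A gaze-anxiety analysis that ignores arm need not lose the ineligible participants: Table 1 does not confine Part 1 eye tracking to eligible people, and section 13e already excludes from Part 1 anyone whose vision prevents it. Randomising all participants also has a cost beyond a few more minutes for non-anxious people. It moves the question from socially anxious people to a general sample. It would also place in the negative-interaction arm people whom section 13e keeps out of Part 2 for current or past bipolar disorder or psychosis.

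**Conclusion.** No change is called for. The timing observation is correct: within Part 1, LSAS and PRCA are pre-randomisation values. The plan would fail only if analysis (1) took them as arm outcomes, and the SAP does not say so. An analyst following the order of events would model Part 1 gaze and SUDS during or after the interaction, with LSAS or PRCA as a covariate or moderator, and would report arm effects as applying to the screened, socially anxious group. On that reading the randomised contrast is valid. The slope of gaze on anxiety is unbiased too, provided the relation is linear and the screening scores that influence gaze are in the model.

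What remains is unwritten detail about measure, timing, role and population, plus a design preference. The cost of restriction is precision and generalisability. Its size depends on an eligible share the documents do not give: slope standard errors about 2.8 to 7.7 times larger for 40% down to 10% eligible on the single-cut assumption. Accepting that cost in order to study socially anxious people is a fair trade-off.

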**Standard Exposure Condition.** Participants in the standard exposure condition will complete Steps 1-4 above but not receive any of the attention guidance components used in the experimental condition.

**Exposure + Attention Control.** Participants in the attention control condition will complete steps 1-4 consist of a unique component where participants will be given a central region of the screen (non-audience member) to focus on.

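### Does analysis (2) need changing because the face rationale and the face target always come together in the guidance arm?

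*SAP*

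**What the plan says.** The SAP's Data Analysis text sets out two analyses. The second is "to compare the attention guidance condition to the other exposure groups", on the PRCA, by Bayesian multi-level models.

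Protocol section 11 (Procedure Description) defines the three exposure conditions. All complete step 1, a psychoeducation video: "This video will explain the intervention, its rationale, and the procedure".

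- **Attention guidance:** "The experimental attention guidance condition consists of three unique components". Two are numbered. The first is that "the intervention rationale will include information about the importance of visually attending to the faces of the audience". The second assigns target audience members to look at, followed by an unnumbered instruction to keep looking at the target throughout the response.
- **Standard exposure:** steps 1-4, but participants do "not receive any of the attention guidance components used in the experimental condition".
- **Exposure + attention control:** steps 1-4, which "consist of a unique component where participants will be given a central region of the screen (non-audience member) to focus on". The rationale shown in this arm is not described.

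Table 1 schedules eye tracking ("EYE-TRACK = Eye tracking data") in Part 1, during the intervention and at both follow-ups. It lists no expectancy or credibility rating. The SAP mentions gaze only in analysis (1): "to compare the positive and negative interactions, where participants are looking, and social anxiety symptoms".

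**The concern.** The study is titled around attention, and an attention-control arm invites the reading that beating it shows something about where people look. In guidance, though, being told that faces matter and being given a face to look at arrive together. Attention control balances having an assigned gaze target, but seemingly not the rationale.

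The outcome is self-reported by people who have heard that rationale. If the rationale alone lowered reported apprehension, guidance could beat both comparators with no contribution from gaze. Agreement between the two contrasts would then look like confirmation although both carry the same rationale effect, and a larger sample would make such a result more likely. No analysis in the SAP separates the two explanations. What is at stake is a mistaken statement about mechanism.

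**Working it through.** **Inputs.** Arm definitions from protocol section 11; the comparison and outcome from the SAP. Neither document gives a per-arm n, rationale effect, baseline correlation or prior. Section 15 gives no statistical basis for the 2,000, so there is no planned figure to reproduce.

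**Step 1: code the arms.** Let R be the face rationale, F the face target against free gaze, and C the central target against free gaze, with additive effects.

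| Arm | Level | R | F | C |
|---|---|---|---|---|
| Guidance | 1 | 1 | 1 | 0 |
| Standard exposure | 1 | 0 | 0 | 0 |
| Attention control | 1 | 0 (inferred) | 0 | 1 |

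The zeros for standard exposure are explicit. R = 0 in attention control is inferred from guidance's components being called unique to it.

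**Step 2: what can be estimated.** The matrix has rank 3 for 4 parameters.

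- Guidance minus standard = R + F.
- Guidance minus control = R + F - C.
- Control minus standard = C.
- Not estimable: R alone, F alone, F - C.

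For example, with C = 0, the pairs (R, F) = (5, 0), (0, 5) and (2.5, 2.5) all give 5 in both guidance contrasts.

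**Step 3: what would change this.** If the attention-control video carried a rationale of equal effect, its row would become (1, 1, 0, 1), and guidance minus control would equal F - C. A fourth arm with the rationale only would make F itself estimable. Even then F is the effect of being assigned a face target, not of looking at it.

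**Step 4: size, illustration only.** Assume F = C = 0, equal allocation, one PRCA occasion, and a flat-prior 95% interval. In SD units, SE = sqrt(2/n) × sqrt(1 - rho²), and the chance that guidance is favoured over attention control is Pr(Z > 1.96 - R/SE).

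With n = 50 per arm, R = 0.2 and rho = 0: SE = sqrt(2/50) = 0.200, R/SE = 1.00, and Pr(Z > 0.96) = 0.169. With rho = 0.7: SE = 0.200 × 0.714 = 0.143, R/SE = 1.40, and Pr(Z > 0.56) = 0.288.

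| R (SD) | One contrast, n = 50 | One contrast, n = 100 | Both contrasts, n = 50 | Both contrasts, n = 100 |
|---|---|---|---|---|
| 0.2 | 17-29% | 29-51% | 7-15% | 15-34% |
| 0.3 | 32-56% | 56-84% | 17-39% | 40-75% |

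Ranges run from rho = 0 to rho = 0.7. The two contrasts correlate 0.5 because they share the guidance arm. With R = 0 the figures are 2.5% for one contrast and 0.5% for both.

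**Step 5: what those figures mean for the planned comparison.** With F = C = 0, the true guidance-minus-control difference is R. At R = 0.2 SD the guidance condition really is 0.2 SD better, and 17-29% is the power to detect it. It is an error rate only for a claim about gaze.

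**Step 6: would the available additions separate R from F?** A model of face gaze by arm, from the eye-tracking data, would show whether guidance participants looked at faces. In the troubling scenario they comply: face gaze is higher under guidance while the benefit comes from the rationale. The check is passed and the misattribution survives. An expectancy rating after the video is likewise observed rather than assigned, and could be collected only from later participants.

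**The case for a change.** The strongest case for a change is that an attention-control arm has little purpose unless the investigators want to say something about attention, so readers will take a win over it as evidence about faces. Stating the limit in advance, reporting the two contrasts separately and tabulating face gaze by arm would cost little and lose no precision on the PRCA.

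Much of this stands. The arms do bundle rationale and target, the rank result is correct, and agreement of the two contrasts is not independent confirmation. Guidance against standard exposure is a package contrast on the protocol's explicit wording.

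Three things limit it.

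- For attention control the result is conditional. That arm also sees a video with a rationale whose content is not described; a rationale of equal effect would cancel. All arms hear some rationale, so the difference is added content about faces rather than a rationale against none.
- The purpose is inferred from the arm's name. Section 36 (Benefits to Society) speaks of understanding the impact of teleconferencing on social anxiety and of designing interventions, not of isolating gaze.
- The low-cost items are wording or description. They neither alter the estimate nor remove the ambiguity.

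The count of three components against two numbered may be a slip: the unnumbered instruction to hold gaze could be the third. It is not evidence of a further hidden difference between arms.

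**Conclusion.** No change to the plan is needed. Analysis (2) validly estimates the effect of the guidance package on the PRCA, which is the comparison the SAP states. A PRCA advantage alone would not tell the face target from the face rationale, and the documents do not say it would.

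The size of any misattribution cannot be fixed from the documents. For an assumed rationale effect of 0.2-0.3 SD and 50-100 per arm, the chance of favouring guidance over attention control runs from 17% to 84%, but this is power for a real difference between conditions. The non-identifiability rests on additive effects and, for the attention-control contrast, on the inference that its video lacks the face rationale.

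Removing the ambiguity would take a matched control rationale or a rationale-only arm. Either is a debatable redesign, and a new control video would help only participants enrolled afterwards. Bundling the components is a fair trade-off for testing a behavioural package.

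Careful analysts would report the two contrasts separately as package effects and could show face gaze by arm as a manipulation check. Saying what rationale attention control receives, and reconciling the component count, would be useful clarifications. None of these alters the analysis or its conclusion.

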**35 Describe debriefing procedures.**

*To input text, click in the light grey area below.*

Participants will be given additional information about the purpose of the study and information about treatment for social anxiety. Participants that are not eligible for or opt-out of the intervention will be debriefed immediately after completing part 1 of the study. If participants complete the intervention component they will be debriefed following the final assessment (week 2 follow-up)

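### Must SAP item (2) name one PRCA contrast, one occasion and one success rule before its primary comparison can be trusted?

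*SAP*

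**What the plan says.** The SAP is one short Data Analysis section. It calls for multi-level models throughout, fitted in a Bayesian framework with brms. Item (2) is "to compare the attention guidance condition to the other exposure groups using the Personal Report of Communication Apprehension as the primary outcome measure".

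The Protocol (section 11, Procedure Description) describes two comparators. Of Standard Exposure it says "Participants in the standard exposure condition will complete Steps 1-4 above", and that those participants will "not receive any of the attention guidance components used in the experimental condition". In Exposure + Attention Control, "participants will be given a central region of the screen (non-audience member) to focus on".

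Table 1 ("PRCA-24 = Personal Report of Communication Apprehension") marks the PRCA-24 in all four columns: Part 1, the intervention, and the 1-week and 2-week follow-ups. The intervention column has one mark, while section 11 says "Participants will complete four intervention (i.e. exposure) sessions within two weeks". The table does not show whether the PRCA is taken once or at each session. Section 35 describes week 2 as the last assessment, but only to time the debriefing.

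Neither document ranks the two contrasts, names a primary occasion or a summary over time, or gives a prior or a posterior threshold. Section 15 (Sample size rationale) refers only to adequate enrolment and completion of Part 2, so it does not point to a particular contrast or occasion.

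**The concern.** A primary outcome measure is not the same thing as a primary result. With two comparators and several PRCA occasions, one fitted model yields many estimates, and any of them could be presented as the trial's answer without departing from item (2). If the choice were made after seeing the data, the chance of a false claim for attention guidance would exceed that of a single named result.

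Using Bayesian methods does not remove this risk: choosing among posteriors after inspecting them is still selection. The two contrasts also answer different questions. One asks whether guidance adds to plain exposure. The other asks whether it differs from directing gaze at a non-audience region. A reader would like to know in advance which one carries the headline.

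**Working it through.** **Figure in the plan.** There is none to reproduce. The documents give no effect size, SD, threshold or power for the PRCA comparison. The total of 2,000 covers Part 1 recruitment and is not derived from it.

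**Counting the candidate results.**
- Pairwise contrasts: 2 (section 11).
- Occasions after Part 1: 1 + 1 + 1 = 3 if the intervention mark means once; 4 + 1 + 1 = 6 if it means every session.
- Results: 2 × 3 = 6 to 2 × 6 = 12.
- If a contrast against both comparators pooled is also counted, which the wording allows: 3 × 3 = 9 to 3 × 6 = 18.
- If each contrast is summarised by one group-by-time effect, which a multi-level model gives naturally: 2.

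The count therefore depends on the reading and is not fixed by the SAP.

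**Cost of picking the best result afterwards.** Assumptions, none in the documents: equal arms, flat prior, success when the posterior probability of benefit exceeds 0.975 (z > 1.96), no true differences, and equal correlation r between PRCA occasions, Part 1 included. The shared guidance arm gives the two contrasts a correlation of 0.5.

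Part 1 PRCA is available and would ordinarily be adjusted for. After adjustment the residual covariance between occasions is r − r² and the residual variance is 1 − r². The correlation becomes (r − r²)/(1 − r²) = r/(1 + r), that is 0.333, 0.412 and 0.474 for r = 0.5, 0.7 and 0.9. The chance that at least one z-score exceeds 1.96, from 1,000,000 multivariate normal draws, is:

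| Candidate results | No baseline adjustment (r = 0.5, 0.7, 0.9) | Adjusted for Part 1 PRCA |
|---|---|---|
| 1 contrast, 1 occasion | 2.5% | 2.5% |
| 2 contrasts, 1 occasion | 4.5% | 4.5% |
| 2 contrasts, 2 follow-ups | 8.1%, 7.4%, 6.3% | 8.5%, 8.3%, 8.1% |
| 2 contrasts, 3 occasions | 11.0%, 9.7%, 7.4% | 11.9%, 11.6%, 11.2% |
| 2 contrasts, 6 occasions | 17.7%, 14.1%, 9.5% | 20.2%, 19.0%, 18.1% |

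These rates apply only when the best result is chosen after the analysis. If all contrasts are reported, none of the individual estimates or intervals is distorted.

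**What naming a single result would buy.** Take as an illustration a true benefit of 0.4 SD and a 90% chance of success on one contrast. Ignoring baseline, n per arm = 2(1.96 + 1.2816)²/0.4² = 131.3, or 132. Adjusting for Part 1 multiplies this by 1 − r²: 98.5, 67.0 and 25.0, or 99, 67 and 25 per arm at r = 0.5, 0.7 and 0.9. These sizes depend on the model and the assumed correlation. Designating a contrast as primary does not change how precisely it is estimated.

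**What it would cost.** Suppose Standard Exposure were tested first and Attention Control only after success. If guidance truly beats Attention Control alone, the first test fails in 1 − 0.025 = 97.5% of trials and the true second claim is formally blocked. The reverse order has the mirror-image cost, and requiring both contrasts to succeed has its own loss of power.

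**The case for a change.** The strongest case for a change is that the omission is genuine and a remedy costs only a few sentences. The SAP template asks for statistical procedures and any power analysis, and the SAP text is complete, so nothing has been blacked out here. A multi-level model estimates every condition-by-occasion effect but does not say which one settles the question. Pooled and slope readings widen the choice rather than narrow it. Adjusting for Part 1 raises the selection risk, to about one in five at six occasions.

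All of that stands as a description. It does not show that the analysis as written gives a wrong answer. The larger figures need the investigators to take whichever result looks best, and at the top of the range to treat PRCA scores from sessions before the end of treatment as candidate primary results. Over the two follow-ups the adjusted figure is 8.1% to 8.5%.

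Any specific wording would also import judgements the documents do not support: which comparator comes first, which occasion, what threshold. The 2-week follow-up looks like the obvious occasion because section 35 says "they will be debriefed following the final assessment (week 2 follow-up", but that sentence concerns debriefing. The documents also do not say whether the follow-up clock runs from the start or the end of an intervention that itself lasts up to two weeks.

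A separate matter is that section 11 says "The experimental attention guidance condition consists of three unique components" and then numbers only two. That is an inconsistency in the intervention description, to be reconciled there. It does not bear on how the PRCA is analysed.

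**Conclusion.** No change follows. The documents leave the primary contrast, the occasion or summary, and the posterior rule unwritten, and this is a gap that analysts can fill sensibly. One model with three conditions by occasion, Part 1 PRCA as baseline, and both contrasts reported with credible intervals falls squarely within item (2) and gives sound estimates.

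The risk depends on selection after the fact. Two contrasts at one occasion carry a 4.5% chance of at least one false success. With baseline adjustment this rises to 11% to 12% over three occasions and 18% to 20% over six. Those figures rest on equal arms, a flat prior, a 0.975 threshold and occasion correlations of 0.5 to 0.9, all assumed. The count of 6 to 12 is itself only one reading, since 2 or 9 to 18 are equally defensible.

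A reader of the results should expect to see both contrasts, and should treat a report that features only one of them, or one isolated occasion, with caution. Data-collection status is not given in the documents, so it cannot be said whether wording added now would precede the analysis.
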